3.4.1 General

For all the key parameters recorded, summary tables including descriptive and/or distribution statistics will be given for both the per protocol analysis and the full analysis data sets.

All enrol participants, defined as subjects who signed the consent form will constitute the safety data set. All subjects who meet the eligibility criteria, adhere to the protocol, and successfully complete the full study assessment will be available for the per-protocol analysis. Participants with missing data will be included in the analysis unless there is some non-response-related reason to exclude them, such as a protocol violation/invalid data.

For continuous variables, the following descriptive statistics will be reported: mean, median, standard deviation, minimum, maximum and sample size. For ordinal variables, the following statistics will be reported: median, mode, minimum, maximum, quartiles, sample size and distribution tables will be produced.

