5.1 Recruitment Procedure

The prospective participants will be selected from the existing clinical population of the OTG-i Research Clinic or recruited by means of an advertisement if necessary. The participants fulfilling the criteria for inclusion and none of the exclusion criteria will be invited in a random fashion to participate in the study until the test population is achieved.

The prospective participants will initially be contacted by telephone, the investigation will be explained in detail and if interested an enrolment / test visit will be scheduled. The prospective participants will be sent a copy of the Participant Information Sheet and Informed Consent by email prior to the visit, upon arrival at the clinic the participants will be given a printed copy of the consent form and the study will be explained to them. The participants will be asked to read and sign the Informed Consent prior to any evaluation.

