5.2 Number of Participants

Up to 40 participants will be screened for 35 participants to be enrolled into the investigational phase at the end of Visit 2 with a view to achieve a cohort of 30 participants completing the study as per the protocol.

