9.2 Procedures for Adverse Events

Treatment of an adverse event will depend on its nature and severity. Based upon the clinical judgment of the investigator the participant may be referred to an ophthalmologist for treatment. The investigator will attempt to determine whether the reaction is related to the eyedrops or a result of other factors. An Adverse Event Form will be completed for each adverse event. If both eyes are involved, each eye will be counted as one adverse event and Adverse Event information will be completed *for each eye*. Whenever possible, the adverse event will be photo-documented.

Expenses incurred for medical treatment as part of study participation will be paid by the sponsor (bills and prescription receipts kept). The participant must be followed until resolution and a written report completed indicating the subsequent treatment and resolution of the condition.

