3.2 Data Sets

Three data sets will be produced as defined below:

- i. Safety Analysis Data Set
Safety analyses will be conducted using this data set. The Safety Analysis Data Set will include all the participants enrolled into the study.
- ii. Full Analysis Data Set

The Full Analysis Data Set will include of all participants who have been exposed to any product evaluated in this study.

iii. Per protocol Data Set

The Per Protocol Data Set will include all the participants who have completed the study as per the protocol, this set will include only participants who have completed the study without any major deviation judged to affect the validity of the data.

Listings and descriptive statistics will be produced for the latter two data sets and comparative statistics will only be produced for the Per Protocol Data Set.

3.3 *Normality Testing*

All primary and secondary endpoints, being continuous endpoints, will be checked for normality graphically and by statistical tests prior to the comparative statistics being carried out. The Q-Q Probability plot will be used to examine the values against a normality distributed data. Statistical (Normality) testing will be carried out by Kolmogorov Smirnov, and Shapiro Wilk tests. The derived histograms and the values of kurtosis and skewness will be taken into consideration when verifying normality and deciding upon the statistical model to use

If the normality assumption does not hold, the data will be transformed; the transformation method chosen will depend upon the skewness and the kurtosis values. The following transformations are the key transformation methods that will be considered for the recorded variables the transformations will be carried in the following order until normality or near normality is achieved: square root, logarithm and inverse. If the data after applying transformations differs statistically from normal, then a non-parametric model will be used.

3.4 *Descriptive Statistics*

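### The safety set is defined by consent rather than by exposure, so adverse event rates for the test regimen, if computed on it, include up to 5 of 40 people who never received the regimen.

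*SAP*

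**What the plan says.** The SAP describes the safety set in two places. Section 3.2 states: "The Safety Analysis Data Set will include all the participants enrolled into the study", and adds: "Safety analyses will be conducted using this data set". Section 3.4.1 says what enrolment means here: "All enrol participants, defined as subjects who signed the consent form will constitute the safety data set". Neither section requires that a participant has used a product.

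Consent comes first in the sequence. Protocol 5.1 states: "The participants will be asked to read and sign the Informed Consent prior to any evaluation". Under Protocol 6.2, the run-in drops then go only to those who meet the criteria at the enrolment visit, and the test products are dispensed at Visit 2, about a week later. Protocol 5.2 gives the planned numbers: "Up to 40 participants will be screened for 35 participants to be enrolled into the investigational phase at the end of Visit 2".

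The one set based on exposure is in SAP 3.2: "The Full Analysis Data Set will include of all participants who have been exposed to any product evaluated in this study". Safety analyses are not assigned to it. After defining the Safety, Full Analysis and Per Protocol sets in that order, the same section says: "Listings and descriptive statistics will be produced for the latter two data sets". That leaves out the safety set, and SAP 3.4.1 and 3.4.2 repeat the restriction.

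On the numerator, Protocol 6.4.2 names the prevalence of adverse events as a safety measure. For an event that affects both eyes, Protocol 9.2 says that "each eye will be counted as one adverse event".

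**The concern.** An adverse event caused by the test regimen can arise only in someone who used it. A denominator fixed at consent also counts people who failed screening and used nothing, and people who used only the run-in drop. Their presence lowers any regimen rate without adding information about the regimen.

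The study has a single arm, so no comparison group shares the dilution. The absolute proportion is what a reader will take away, which makes the choice of denominator matter more than it would in a randomised comparison.

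Three further points are unsettled. The SAP does not say whether run-in events and regimen events are tabulated apart. It does not say whether a rate counts participants, eyes or events. It also sends the safety analyses to one set while promising descriptive output only for the other two.

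**Working it through.** The readable text gives no adverse event rate, so there is no figure of the plan's own to reproduce. The check uses its planning numbers.

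**Inputs**
- Screened: up to 40 (Protocol 5.2). Consent precedes any evaluation (Protocol 5.1), so I take everyone screened as having signed, which puts up to 40 in the safety set.
- Entering the investigational phase at the end of Visit 2, when the test products are dispensed: 35 (Protocol 5.2 and 6.2). I take all 35 as recipients of the regimen.
- Never received the regimen: up to 40 − 35 = 5. The documents do not say how many of these failed at Visit 1 (no product) and how many left between Visits 1 and 2 (run-in drops only).

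**Effect on a regimen rate counted per participant**

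If x recipients have at least one regimen event, the rate on the safety set is x/40 and the rate among recipients is x/35. The ratio is (x/40)/(x/35) = 35/40 = 0.875, a relative understatement of 1 − 0.875 = 12.5% whatever x is.

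| Participants affected | On 40 | On 35 | Gap (points) |
|---|---|---|---|
| 1 | 2.5% | 2.9% | 0.4 |
| 5 | 12.5% | 14.3% | 1.8 |
| 8 | 20.0% | 22.9% | 2.9 |

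**If fewer than 40 consent for the same 35 recipients**
- 36 consent: 35/36 = 0.972, an understatement of about 3%.
- 39 consent: 35/39 = 0.897, an understatement of about 10%.

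So 12.5% is a ceiling at the planned numbers.

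**Whether the overall figure must be too low**

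It need not be, because the numerator can move as well.
- Suppose 5 recipients have a regimen event and one run-in-only participant also has an event. The pooled figure is 6/40 = 15.0%, above 5/35 = 14.3%.
- Suppose 5 recipients each have a bilateral event. Under Protocol 9.2 that is 10 events, and 10/40 = 25.0% if events are divided by people.

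Both cases are illustrations. They show that the sign of the net error depends on choices that the SAP leaves open.

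**Whether the other definitions settle it**
- SAP 3.2 on its own could give 35, if enrolled meant entry into the investigational phase, as in Protocol 5.2 and SAP 2.3. SAP 3.4.1 rules that out for the safety set by tying enrolment to consent.
- The Full Analysis Set turns on which products count as evaluated. SAP 2.4 lists only the daytime drop and the night gel as study products, and Protocol 4.1 and 4.2 separate test products from the run-in product. This favours test-regimen exposure. However, Protocol chapter 4 places both under test materials, so the point is not closed.

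**The case against.** A reader might infer that the plan divides regimen event rates by 40 and so biases them downward. The documents do not go that far. No readable section gives a formula for an adverse event rate. The denominator follows only from joining the safety-set rule in SAP 3.2 and 3.4.1 to the prevalence measure in Protocol 6.4.2, and the sentences on descriptive output point to the other two sets. The downward direction holds only for regimen events counted per participant. Pooled run-in events or eye-level counts can push the figure up.

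A reader might also infer that run-in and regimen events cannot be told apart. That is too strong. Protocol 9.2 requires a form for each event, Protocol 12.1 describes case report forms built for each visit, and Visit 2 divides the two periods. The SAP is silent on tabulating by period, but nothing shows that the data could not be split.

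Three more objections have force. The Full Analysis Set may already mean exposure to the test regimen. A consent-based set has a rationale, since Protocol 9.3 collects serious events from signature of the consent form. And the effect is small beside sampling error: the exact 95% interval for 5/35 runs from 4.8% to 30.3%, against a gap of 1.8 points, and the readable plan tests no safety hypothesis.

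These points narrow the concern but do not remove it. The SAP states a set for safety analyses, that set has no exposure condition, and following the rule as written puts people without the regimen into the denominator. Collecting and listing events from consent is sound. Using consent as the base for a regimen rate is not.

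**Conclusion.** The point holds as a minor, cheaply corrected flaw. If prevalence is computed on the safety set as SAP 3.2 and 3.4.1 define it, the rate of regimen events per participant is understated by at most 12.5% in relative terms, and by about 3% to 10% if 36 to 39 people consent. This assumes that everyone screened has consented, that 35 people receive the regimen, and that the numerator counts participants with a regimen event.

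The direction of an overall adverse event figure is not established. Separately, assigning safety analyses to one set while limiting listings and descriptive statistics to the other two is a conflict within the SAP, and it needs resolving whatever denominator is chosen. None of this affects the efficacy conclusions, whose comparative statistics use the Per Protocol set.

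**What to change.** Keep a listing of all adverse events from signature of consent, for everyone who signed, with events before first product use marked as such. Base the rates on exposure, and name the product each time:

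- Run-in period: events from first use of the run-in drops up to dispensing at Visit 2, over participants who received the run-in drops.
- Regimen period: events from Visit 2 onward, over participants who received at least one of the two test products.

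A general phrase such as at least one dose of a study product would bring back the ambiguity in the Full Analysis Set definition. State there too whether run-in-only participants belong.

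Make participants with at least one event the main summary, and give eye-level counts, as recorded under Protocol 9.2, as a second line. Use enrolled in one sense throughout the SAP. Amend SAP 3.2, with 3.4.1 and 3.4.2 to match, so that safety summaries are produced for these exposure-based sets.

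The cost is SAP wording and one extra table column. Events must be dated well enough to place them before or after Visit 2. Regimen rates per participant may look slightly less favourable than on the consent-based set.

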3.4.2 Output

The descriptive statistics will be reported both for the full analysis population and the per protocol population.

3.5 *Comparative Statistics*

3.5.1 General

The study design does not include a control group the efficacy of the regimen will be measured by comparing the data recorded at the dispensing visit, prior product dispensing visit (Baseline) to the data recorded at the 30-Day follow-up visit (Response).

In this study two sets of analyses will be carried out for each primary and secondary variables. The first set will follow a linear model approach to account for all the data characteristics (e. g. multiple data for the same response variable for a given timepoint). The second set will be based on simplistic testing such as the t-test or if not applicable an equivalent non-parametric test.

3.5.2 Primary Endpoints

LINEAR MODEL ANALYSIS

The primary variables OSDI total score and measured lissamine green bulbar conjunctival staining are parametric variables.

The primary variables being continuous variables ideally parametric testing will be carried out. Therefore, if the variables are normality distributed or close to normally distributed before or after transformation allowing parametric analysis parametric statistics will be carried out using the following model:

OSDI Total Score: A linear mixed model will be used. The model will include time (Baseline / Dispensing visit, One-month follow-up visit) as repeated measures fixed factor. The subject ID will be a random factor. The covariance structure that best models the residuals errors from the same subject across the time periods will be selected according to the AICC criterion. Possible structures will include Compound Symmetry (CS), Heterogeneous Compound Symmetry (CSH), Ante-Dependent (ANTE (1)), Autoregressive (AR1), Unstructured (UN). In case that the Hessian Matrix is not positive definite, random effect will be removed from the model. The comparisons of OSDI scores between baseline and one month follow up will be carried out using a 95% confidence interval from the least square mean differences in percentage from the mixed linear model.

Lissamine green bulbar conjunctival staining: A linear mixed model will be used. The model will include time (Baseline / Dispensing visit, One-month follow-up visit), region (nasal and temporal) as repeated measures fixed factors as well as with all the possible interactions. The eye will be taken into consideration as repeated measure but not as fixed factor. The subject ID will be a random factor. The covariance structure that best models the residuals errors from the same subject across the time and eye will be selected according to the AICC criterion. Possible structures will include Compound Symmetry (CS), Heterogeneous Compound Symmetry (CSH), Ante-Dependent (ANTE (1)), Autoregressive (AR1), Unstructured (UN). In case that the Hessian Matrix is not positive definite, random effect will be removed from the model. The comparisons of Lissamine green bulbar conjunctival staining between baseline and one month follow up will be carried out using a 95% confidence interval from the least square mean differences in percentage from the mixed linear model.

If the variables cannot be normalized the following model will be applied:

OSDI Total Score: A generalized mixed linear model will be used. Possible models will include Gamma regression model with a Log link function or a Negative Gaussian with Log link function. The model will include time (Baseline / Dispensing visit, One-month follow-up visit) as repeated measures fixed factors. The subject ID will be a random factor. The covariance structure that best models the residuals errors from the same subject across the time and eye will be selected according to the AICC criterion. Possible structures will include Compound Symmetry (CS), Heterogeneous Compound Symmetry (CSH), Ante-Dependent (ANTE (1)), Autoregressive (AR1), Unstructured (UN). In case that the Hessian Matrix is not positive definite, random effect will be removed from the model. The comparisons of OSDI score between baseline and one month follow up will be carried out using a 95% confidence interval from the least square mean differences in percentage from the generalized mixed linear model.

Lissamine green bulbar conjunctival staining: A generalized mixed linear model will be used. Possible models will include Gamma regression model with a Log link function or a Negative Gaussian with Log link function. . A linear mixed model will be used. The model will include time (Baseline / Dispensing visit, One-month follow-up visit), region (nasal and temporal) as repeated measures fixed factors as well as with all the possible interactions. The eye will be taken into consideration as repeated measure but not as fixed factor. The subject ID will be a random factor. The covariance structure that best models the residuals errors from the same subject across the time and eye will be selected according to the AICC criterion. Possible structures will include Compound Symmetry (CS), Heterogeneous Compound Symmetry (CSH), Ante-Dependent (ANTE (1)), Autoregressive (AR1), Unstructured (UN). In case that the Hessian Matrix is not positive definite, random effect will be removed from the model. The comparisons of Lissamine green bulbar conjunctival staining between baseline and one month follow up will be carried out using a 95% confidence interval from the least square mean differences in percentage from the generalized mixed linear model.

SIMPLISTIC SINGLE FACTOR ANALYSIS

The primary variables OSDI total score and measured lissamine green bulbar conjunctival staining are parametric variables.

The primary variables being continuous variables ideally parametric testing will be carried out. Therefore, if the variables are normality distributed or close to normally distributed before or after transformation allowing parametric analysis parametric statistics the following test will be applied:

OSDI Total Score: A paired t-test approach will be followed. The test will compare the OSDI scores recorded at the two visits (Baseline / Dispensing visit, One-month follow-up visit). The comparisons of the OSDI scores between baseline and one month follow up will be carried out taking 95% as the threshold of significance.

Lissamine green bulbar conjunctival staining: A paired t-test approach will be followed. Lissamine green bulbar conjunctiva staining is recorded and quantified separately for the right and left eyes and for the nasal and temporal bulbar regions; therefore, in order to prevent sample size overestimation by accounting for each measurement the analysis will be carried out on the mean staining of the two zones of the two eyes to have a single data point per visit. The test will compare the mean staining recorded at the two visits (Baseline / Dispensing visit, One-month follow-up visit). The comparisons of the mean staining between baseline and one month follow up will be carried out taking 95% as the threshold of significance.

If the variables cannot be normalized the following test will be applied:

OSDI Total Score: the non-parametric equivalent of the paired t-test is Wilcoxon Rank Test. The test will compare the OSDI scores recorded at the two visits (Baseline / Dispensing visit, One-month follow-up visit). The comparisons of the OSDI scores between baseline and one month follow up will be carried out taking 95% as the threshold of significance.

Lissamine green bulbar conjunctival staining: the non-parametric equivalent of the paired t-test, is Wilcoxon Rank Test. The test will compare the mean staining of the two measurement zones of the two eyes to produce a single data point per visit (Baseline / Dispensing visit, One-month follow-up visit). The comparisons of the mean lissamine green staining between baseline and one month follow up will be carried out taking 95% as the threshold of significance.

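### The SAP does not say which of two staining analyses decides, and its mixed model names no participant-by-visit term and leaves region's place in the covariance unclear, so its interval may be too narrow if participants' changes differ

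*SAP*

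**What the plan says.** SAP 3.5.1 states: "In this study two sets of analyses will be carried out for each primary and secondary variables". Of the linear model it says: "The first set will follow a linear model approach to account for all the data characteristics". It does not say which set gives the trial's result.

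For staining, the SAP 3.5.2 mixed model has time and "region (nasal and temporal) as repeated measures fixed factors as well as with all the possible interactions". On eye and the random part: "The eye will be taken into consideration as repeated measure but not as fixed factor. The subject ID will be a random factor". On the residual covariance: "The covariance structure that best models the residuals errors from the same subject across the time and eye will be selected according to the AICC". The candidates are CS, CSH, ANTE(1), AR1 and UN, and the random effect is dropped if the Hessian is not positive definite. The model is read by its own criterion: "The comparisons of Lissamine green bulbar conjunctival staining between baseline and one month follow up will be carried out using a 95% confidence interval".

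The simpler analysis in the same section averages the two zones of the two eyes: "in order to prevent sample size overestimation by accounting for each measurement the analysis will be carried out on the mean staining". It also has its own criterion: "The comparisons of the mean staining between baseline and one month follow up will be carried out taking 95% as the threshold of significance".

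SAP 2.2 states the staining hypothesis in one direction, a decrease. Some SAP pages were not available for review, so the absence of a ranking refers to the visible text.

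**The concern.** Each participant gives 2 visits × 2 eyes × 2 regions = 8 staining values. The contrast of interest is between visits. If some participants improve more than others, all four values at a visit shift together within a person, and the error of the mean change is governed by the number of people. A model with only a participant intercept, or CS, treats that shared shift largely as independent noise across zones. The SAP recognises this hazard for the paired test, where it averages, but names nothing in the mixed model that guards the visit contrast.

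Region adds a second uncertainty. It is called a repeated measures factor, yet the covariance runs over time and eye only. If region lies outside the block, even UN cannot carry a visit shift shared by both regions.

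The result for a primary endpoint could therefore depend on which of two unranked analyses is reported.

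**Working it through.** **The plan's own figure.** The only power statement (Protocol 7.1) is for OSDI. Effect (10.0 − 7.5)/5.0 = 0.5, n = 27, one-sided 0.05 and 26 df give power 0.812, which reproduces the stated 81%. The documents give no variance or power for staining.

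**Inputs.** From the documents: 30 completers, 8 values each, fixed effects time, region and time × region, and the five candidate structures. Assumed: normal data, no true change, participant variance 1, residual e = 0.5, participant-by-visit variance a, and participant-by-zone variance z (a zone is one region of one eye).

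**Step 1, correct error.** Each participant's change in mean staining has variance 2a + 2e/4 = (e + 4a)/2. The paired test on the participant mean estimates this directly, with 29 df.

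**Step 2, CS with all eight values in the block.** CS pools the within-person mean squares: visit (1 of 7 df, e + 4a), zone (3 df, e + 2z) and visit × zone (3 df, e). The average is e + (4a + 6z)/7, so

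model width / correct width = √{[e + (4a + 6z)/7] / (e + 4a)}.

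For a = 0.2, z = 0.5: √[(0.5 + 3.8/7)/1.3] = √(1.043/1.3) = 0.90. The critical value is 1.97, on 30 × 7 − 3 = 207 df. Putting the ratio straight into a normal tail gives 7.7% error for that pattern; allowing for sampling error in the pooled variance gives 7.9%. The CS row below uses the second method.

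**Step 3, region outside the block.** Under UN over time and eye, each region's visit difference has variance 2a + e, and 60 such differences are treated as independent, apart from the participant intercept. The true/model SE ratio is √[(e + 4a)/(e + 2a)]: 1.00, 1.20 and 1.29 at a = 0, 0.2 and 0.5.

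**Step 4, AICC selection.** REML fits of all five structures with Satterthwaite df, 2,500 null trials per pattern. Monte Carlo SE is 0.4 points at 5% and 0.7 at 15%.

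| (a, z) | (0, .5) | (.2, .5) | (.5, .5) | (.2, .1) | (.5, .1) |
|---|---|---|---|---|---|
| CS width ratio | 1.36 | 0.90 | 0.70 | 0.73 | 0.59 |
| CS two-sided error, % | 0.8 | 7.9 | 17.2 | 15.0 | 24.7 |
| Selected coverage, region in, % | 95.2 | 90.2 | 87.4 | 87.2 | 85.2 |
| Selected coverage, region outside, % | 93.0 | 87.7 | 84.6 | 83.4 | 82.6 |
| False benefit, region in, % | 2.5 | 5.0 | 5.6 | 6.1 | 7.2 |
| False benefit, region outside, % | 3.6 | 6.0 | 7.6 | 8.2 | 8.7 |

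False benefit is the share of null trials showing a significant decrease. The paired t-test on the same data rejected in 1,254 of 25,000 trials, or 5.0% two-sided. Forcing 29 df on the model changed its error by at most 1.3 points.

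**Step 5, disagreement.** One analysis was significant and the other not in 4.6 to 9.7% of null trials with region in the block (116 to 242 of 2,500) and 4.0 to 12.8% with it outside (101 to 321).

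**Step 6, cell order.** AR1 and ANTE(1) over eight cells depend on their order, which the SAP does not state. The region-in rows used one time-first order. In smaller runs of 400 trials at (.2, .5), selected-model error was 7.3% with the visit-1 cells placed first and 14.8% with visits alternating within zone; the paired t-test gave 5.5% in both.

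**The case against.** The strongest reply is that the plan already contains a sound test and a structure able to carry the variation. The participant-mean test is planned, and UN over all eight values can represent a participant-by-visit shift. The first point stands and makes the fix cheap, but the test protects the result only if it decides. The second stands in part. UN is one of five candidates and has 8 × 9/2 = 36 parameters for about 30 people (240 values). In a separate check without zone variance, AICC chose it in 0% and 2.4% of runs when changes differed. Fitted regardless of AICC with region in the block, it still had 8.7 to 9.7% error. With region outside, Step 3 applies.

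It is also fair that the variances are assumed, that a = 0.2 and 0.5 are 40% and 100% of the residual variance, and that the region-in rates move with cell order. They show direction and rough size only. At a = 0.1 (1,000 trials) coverage was milder with region in the block, 93.1 and 90.1%, and 88.6 and 86.7% outside (z = 0.5 and 0.1).

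Finally, the hypothesis is directional. Against the 2.5% implied by a two-sided 95% interval, false benefit is inflated once changes differ. Against the one-sided 0.05 stated for OSDI, it runs from below to moderately above nominal. A reader might take the two-sided coverage loss as the size of the decision error; the directional figures do not support that.

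**Conclusion.** The concern holds in conditional form. Three facts come from the text and need no variance assumption: the two staining analyses are unranked, no participant-by-visit term is named, and region's place in the covariance is unclear.

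The effect on the interval depends on quantities that the documents do not give. If participants' changes differ, the interval may be too narrow: coverage falls to roughly 82 to 90% over the main assumed patterns, and CS alone has up to 24.7% two-sided error. If changes do not differ, the selected interval is near nominal (93.0 to 95.2%), but CS is too wide when zones differ stably, with 0.8% error.

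A reader might infer that the mixed-model interval is certain to be wrong. Without staining variances or a stated cell order, the documents do not support that. A reader might also take the disagreement between analyses as opposite conclusions about the treatment; it means only that one is significant and the other is not. The plan should be changed, at little cost, but the point does not invalidate the staining endpoint.

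**What to change.** In SAP 3.5.1 and 3.5.2, name the participant-mean paired comparison (Wilcoxon if normality fails) as the decisive staining analysis and the mixed model as supportive. Use the same ranking for the generalized-model fallback. That is for consistency only, as the fallback was not simulated.

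If the supportive model is kept, for staining:

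- replace the AICC-selected residual structure with participant, participant-by-visit and participant-by-zone random effects, independent residuals, and Satterthwaite or Kenward-Roger degrees of freedom;
- state that all eight values lie in the participant's block;
- state that the rule removing the random effect does not apply to the participant-by-visit term, since that rule could otherwise delete it;
- if the model does not converge, report the participant-mean analysis alone.

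On data simulated from these same components (100,000 draws), this model had 4.1, 5.0, 5.0, 5.0 and 4.9% error over the five patterns. That checks consistency and is not independent proof.

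The cost is SAP wording and a possibly wider supportive interval. Inverting the Step 2 ratios, the correct width is 0.73 to 1.69 times the CS width in the assumed patterns. No new data are needed, and the decisive test is already planned.
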